14.1.2 Specification of source data and source documents

Source documents provide evidence for the existence of the participant and substantiate the integrity of the data collected. Source documents are filed at the investigator site.

Data reported on the CRF or entered in the CRF that are from source documents must be consistent with the source documents or the discrepancies must be explained. The investigator may need to request previous medical records or transfer records, depending on the study. Also, current medical records must be available.

14.1.3 Archiving of essential clinical investigation documents

See section 14.1.

14.2 Data management

For all subjects enrolled in the study, site staff will promptly complete and allow Hemanext and/or its designees' access to all case report forms (CRFs) required for the study in the form supplied by the Sponsor or its designee. Site staff will not be required to disclose information in CRFs which would permit identification of a subject enrolled in, or a candidate for, the study. CRFs will be provided to Hemanext or its designees in a medium specified by Hemanext or its designee. At the request of Hemanext or its designees, sites will promptly correct any errors and/or omissions to the CRFs for the study and will make available to the Sponsor and/or its designees the corrected CRFs and supporting records for further verification. Investigator agrees to sign/e-sign a statement in each subject's study records or CRF attesting to his/her review of the CRF and verifying that the information included on such form is accurate and includes the treatment, care, and events surrounding such subject's involvement in the study.

Sites will retain organized subject, laboratory, and study device inventory records relating to the study for the period of time required by applicable federal law or regulation. The site will not destroy such records without giving the Sponsor prior written notice and the opportunity to further store such records, at the Sponsor's cost and expense. Case Report Forms will be retained for a minimal period of 15 years after completion of the study. Clinical records kept by the Sponsor will be held in locked cabinet.

14.2.1 Data Management System

Refer to Data Management Plan.

14.2.2 Data security, access and back-up

Refer to Data Management Plan.

14.2.3 Analysis and archiving

Refer to Data Management Plan.

14.2.4 Electronic and central data validation

Refer to Data Management Plan.

14.3 Monitoring

Monitoring will be conducted by the sponsor or delegate according to clinical monitoring SOPs to assure that the protocol is followed, any adverse events are reported, data collected are scientifically sound, and that the study is conducted in compliance with ICH Good Clinical Practice, ISO, and MDR guidelines. On-site monitoring visits will occur at study initiation, during the study performance as needed (minimum one interim visit) and at the study close.

On-site monitoring visits will take place at each center at study initiation, during the course of the study (as long as there are patients in follow up at the site) at the frequency defined in the monitoring plan, and for the final visit at the close of the study. The initiation visit is intended to provide an opportunity for the monitor to review the Investigational Plan with the Investigators and to ensure that the Investigators:

- 1. have appropriate training, facilities, patient load, time, and willingness to comply with study requirements;
- 2. have the approval of the supervising CEC for the Investigational Plan;
- 3. have all study documentation and required records on site; and
- 4. assume responsibility for the investigation at their center.

Visits during the study are intended to assess Investigators' adherence to the Investigational Plan, maintenance of records, reports and investigational devices, and review of source documents for accuracy, completeness, and legibility. During these study visits, the monitor is required to assess the progress of the study toward meeting study objectives, and to identify any concerns that stem from observations of device performance and/or review of the Investigator's patient records, study management documents, and informed consent documents, and to ensure accountability of all patients that have been treated under the study.

The monitor's final on-site visit at completion of the study is intended to assure that all the data have been properly completed and to have a closing meeting with the Investigators and their staff members. Reports of the on-site visits will be made by the monitor and should include resolution of concerns, completion of appropriate follow-up activities, completion of assigned tasks, and any necessary corrective actions. At the close of the study, the monitor will prepare a final report.

14.4 Audits and Inspections

The sponsor retains the right to audit any investigational site for the duration of this clinical investigation.

All investigators do guarantee access to their site and source data for monitors, auditors, or inspectors of the competent administrative authority.

14.5 Confidentiality, Data Protection

All parties will comply with all applicable laws, including laws regarding the implementation of organizational and technical measures to ensure protection of participant data.

Participants' personal data will be stored at the study site in encrypted electronic and/or paper form and will be password protected or secured in a locked room to ensure that only authorized study staff have access. The study site will implement appropriate technical and organizational measures to ensure that the personal data can be recovered in the event of disaster. In the event of a potential personal data breach, the study site will be responsible for determining whether a personal data breach has in fact occurred and, if so, providing breach notifications as required by law.

To protect the rights and freedoms of participants with regard to the processing of personal data, participants will be assigned a single, participant-specific numerical code. Any participant records or data sets that are transferred to the sponsor will contain the numerical code; participant names will not be transferred. All other identifiable data transferred to the sponsor will be identified by this single, participant-specific code. The study site will maintain a confidential list of participants who participated in the study, linking each participant's numerical code to his or her actual identity and medical record identification. In case of data transfer, the sponsor will protect the confidentiality of participants' personal data consistent with the clinical study agreement and applicable privacy laws.

14.6 Storage of biological material and related health data

Not applicable.

No biological material and/or related health data from the participants will be stored for the purpose of this clinical investigation.

15. PUBLICATION AND DISSEMINATION POLICY

The results of this study may be published or presented at scientific meetings by the investigator after publication of the overall study results or 1 year after the end of the study (or study termination), whichever comes first.

The investigator agrees to refer to the primary publication in any subsequent publications, such as secondary manuscripts, and submits all manuscripts or abstracts to the sponsor 30 days before submission. This allows the sponsor to protect proprietary information and to provide comments and the investigator will, on request, remove any previously undisclosed confidential information before disclosure, except for any study or Hemanext intervention related information necessary for the appropriate scientific presentation or understanding of the study results.

For all publications relating to the study, the investigator will comply with recognized ethical standards concerning publications and authorship, including those established by the International Committee of Medical Journal Editors.

The sponsor will comply with the requirements for publication of the overall study results covering all investigator sites.

Authorship of publications for the overall study results will be determined by mutual agreement and in line with International Committee of Medical Journal Editors authorship requirements.

If publication is addressed in the clinical study agreement, the publication policy set out in this section will not apply.

16. FUNDING AND SUPPORT

16.1 Funding

As the sponsor of the study, Hemanext, Inc. will provide all the funding for this investigation.

16.2 Other Support

Not applicable.

17. INSURANCE

Insurance will be provided by the Sponsor. A copy of the certificate is filed in each investigation site file and the sponsor's Trial Master File.

19. APPENDICES

19.1 **Investigator Brochure** Document provided separately.

19.2 Hemanext Storage Bag (HSB) labelling

19.3 Hemanext ONE Instructions for Use

IFU Reference: LBL-194-0057 revision E01

| HGB | Hemoglobin |
| ICH | International Council on Harmonization |
| IMP | Investigational medicinal product |
| MDS | Myelodysplastic Syndromes |
| MedDRA | Medical Dictionary for Regulatory Activities |
| PPAS | Per-protocol analysis set |
| RBC | Red blood cell |
| SAP | Statistical analysis plan |
| SADE | Device deficiency with Serious Adverse Device Effect |
| SADE | Serious Adverse Device Effect |
| SAE | Serious Adverse Event |
| TBSA | Total Body Surface Area |
| USADE | Unanticipated / Unexpected Serious Adverse Device Effect |
| VS | Vital Signs |
| WHO | World Health Organisation |

1 Acronyms and Abbreviations used in the Document

2 Introduction

The Statistical Analysis Plan (SAP) is a complementary document to the Clinical Study Protocol and includes a more technical and detailed elaboration of the principal features of the proposed statistical analysis and presentations, and the way in which anticipated analysis problems will be handled.

If the SAP suggests changes to the principal features stated in the protocol, these should also be documented in a protocol amendment. Otherwise, it will suffice to record the changes in the SAP.

3 Study Objectives

3.1 Primary Objective

A. For both patient groups

To assess the safety and tolerance of Hypoxic RBCs up to 24 hours following the transfusion initiation and overall, up to 7 days (+/- 1 day) after the transfusion episode (single transfusion course).

3.2 Secondary Objectives

- B. For both patient groups
 - 1. Assessment of pre and post transfusion hemoglobin levels
 - 2. Assessment of hemoglobin level before the following transfusion, if applicable
 - 3. Assessment of AEs occurrence:
 - i. Up to 7 days (+/- 1 day) post transfusion (including but not limited to infection, deep vein thrombosis, acute respiratory distress syndrome, transfusion-related acute lung injury, transfusion associated circulatory overload, anaphylactic shock, acute haemolytic transfusion reaction).
 - ii. Up to the subsequent transfusion episode or up to 28 days (+/- 1 day) after the initial transfusion, whichever comes first.
 - iii. From enrolment, up to their subsequent transfusion or 28 days (+/- 1 day) post transfusion, whichever comes first, through the assessment of patient's diary
 - 4. Assessment of the Vital Signs (VS) during and up to 15 minutes after the transfusion
- C. For burn patient group only:
 - 1. Assessment of arterial blood gases:
 - i. pre-operative
 - ii. intra-operative
 - iii. post operative

3.3 Clinical investigation outcomes

3.3.1 **Primary outcome**

Number of participants who experienced an adverse event (all types/grades) from transfusion up to 24 hours and 7 days (+/- 1 day) post transfusion.

3.4 Secondary Outcomes:

1. Evaluation of blood pH, pO2, pCO2, HCO3 and base (excess) before, during and after the transfusion (Burn patients group only).

LINK Medical Study ID: HEM001

- 2. Hemoglobin level before the following transfusion
- 3. Frequency of all AEs, including transfusion related AEs up to 7 days (+/- 1) post-transfusion
- 4. AEs up to 28 days after the initial transfusion, or up to subsequent transfusion episode, whichever comes first.
- 5. Frequency of all AEs, from enrollment, up to 7 days (+/- 1 day) post transfusion, through the assessment patient's diary, when applicable.
- 6. Vital signs over the course of the transfusion and up to 15 minutes post-transfusion.

4 Study Design

This is a single center clinical trial of surgical bleeding in burn patients, and chronically transfused patients with haematologic malignancies. Patients are transfused with hypoxic red blood cells manufactured with Hemanext ONE system". The patient groups are burn patients and chronically transfused patients with haematologic malignancies. Patients need to be adults \geq 18. There will be no randomization of Patient s, no blinding, and no comparator.

A first cohort of 5 patients – solely from the hematological malignancies (chronically transfused) group - will be enrolled, transfused and followed-up until their subsequent transfusion or 28 days (+/- 1 day) post-transfusion, whichever comes first. All safety related data from this initial cohort of 5 patients will be reviewed and assessed by the clinical investigation Data Monitoring Committee (DMC). Upon favourable opinion from the clinical investigation DMC, the enrolment of the remaining patients (both groups) will resume until completion.

Each patient is expected to attend 5 visits:

- 1. Visit 1 (Screening): Determine eligibility and obtain baseline data, physical examination, and safety assessments.
- 2. Visit 2 (Transfusion Day):
 - a. Pre-Transfusion: eligibility, hemoglobin, and safety assessments
 - b. Transfusion: transfusion, safety assessments, and device integrity
 - c. Post-Transfusion: safety assessments, hemoglobin, and device integrity
- 3. Visit 3 Follow-Up (24 hours post-transfusion): safety assessments and device integrity
- 4. Visit 4 Follow-Up (7 days (+/- 1) post-transfusion): safety assessments, and device integrity
- 5. Visit 5- Final Follow-Up (28 days (+/- 1 day)): hemoglobin and physical examination

A complete study flow chart for Hematogical Malignancies Group is presented in Appendix A: and a complete study flow chart for Burn patients Group in Appendix B: .

5 Study Population

The study population consist of two sperate groups of adult patients (\geq 18) male and female:

- 1. Acute burn patients, hospitalized with a Total Body Surface Area (TBSA%) burn ≥ 10% and ≤50% expected to require > 2 unit of red blood cells in a single transfusion event.
- Hematologic malignancies patients identified by a Transfusion hemoglobin trigger of less than 9 g/dL with a documented diagnosis of leukemia, myelomatosis or myelodysplastic syndromes (MDS) and requiring chronic transfusions. Patients expected to require > 2 units of red blood cells in a single transfusion event.

LINK Medical Study ID: HEM001

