6.2 Primary Objective

Primary Objective – for both patients groups

Hypoxic RBCs safety and tolerance assessment up to 24 hours following the transfusion initiation and overall up to 7 days (+/- 1 day) after the transfusion episode (single transfusion course).

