7. CLINICAL INVESTIGATION OUTCOMES

7.1 Primary Outcome

Primary Outcome – for both patients groups

Number of participants who experienced an adverse event (all types/grades) within a time frame up to 24 hours following the transfusion and overall up to 7 days (+/- 1 day) after the transfusion.

The type and the grade of each adverse event will be categorized according to:

- Association for the Advancement of Blood and Biotherapies (AABB) technical manual, 20th edition (2020)
- Biomedical Excellence for Safer Transfusion (BEST) Collaborative review Lancet 2016; 388: 2825–36
- Local AEs database (for reference)
- ISO 14155-2020 definitions

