10.1.1 Experimental Intervention (medical device)

Units of hypoxic RBCs will be manufactured at Oslo's University Blood Bank or Haukeland University Hospital's Blood Bank using Hemanext ONE system. The hypoxic RBCs manufactured in Oslo will be shipped to the Blood Bank at Haukeland University Hospital where they will be stored at 1-6°C for up to 42 days. Participants who would normally receive a transfusion of units of conventional RBCs will instead receive a transfusion of 2 units of hypoxic RBCs and any additional conventional RBCs as needed. All transfusions will be performed according to the site's SOPs.

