11.2.1 Assessment of primary outcome

Patients will be monitored for adverse events throughout the entirety of their participation in the clinical investigation. Investigators will monitor patients directly for adverse events during their transfusion visit. In addition, patients will be contacted by phone 24 hours and 7 days (+/- 1) after their transfusion visit to record any adverse events they have experienced since their transfusion visit. All adverse events will be recorded in the CRF and they will be assessed according to the instructions in section 12 of the CIP.

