12.2 Documentation and reporting in Medical Device clinical investigations

Device deficiencies and all **adverse events (AE)** including all **serious adverse events (SAE)** are collected, fully investigated and documented in the source document and appropriate CRF during the entire investigation period, i.e. from patient's informed consent until the last CIP-specific procedure, including a safety follow-up period.

- Documentation of AEs (including SAEs) by the PI includes diagnosis or symptoms, start and stop dates of event, event treatment, event resolution, assessment of seriousness and causal relationship to MD and/or investigation procedure (ISO14155).
- Documentation of DDs by the PI includes description of event, start date, investigational device information, action taken with regard to the investigational device, and whether the DD led to an AE. The Sponsor shall review all DDs and determine and document in writing whether they could have led to a SAE (DD with SADE potential) (ISO14155).

The Sponsor provides the CEC with the documentation at their request

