12.8 Procedure

12.8.1 Initiation of Adverse Event Reporting

The Clinical Project Manager or designee will train the investigator and staff regarding the recording and reporting of adverse events. The sponsor shall implement and maintain a system to ensure that the reporting of the reportable events will be provided by the investigator to the sponsor immediately, but not later than 3 calendar days after investigation site study personnel's awareness of the event.

Adverse events (AEs) are recorded on the CRF by the sites. The following information should be recorded:

- The description of the event with enough detail to determine if the event meets the definition of a serious adverse event
- The date of the onset of the adverse event
- Relevant medical history leading up to the event
- A description of the action to treat the adverse event
- The site will also classify the event using the scales below

The investigator shall determine the AE Severity using the following scoring system which will be included on the CRF. The severity score is necessary is used to determine if the event meets the definition of a serious adverse event. The rating may also be used to determine if an adverse device event is unanticipated. This may be the case if the severity is greater than previously identified.

Rating	Description	Definition
5	Catastrophic	Patient Death
4	Critical	Permanent impairment or life threatening injury
3	Serious	Injury requiring medical intervention to prevent permanent impairment
2	Minor	Temporary injury that does not require medical intervention
1	Negligible	Inconvenience or temporary discomfort

The relationship between the use of the medical device (including the medical – surgical procedure) and the occurrence of each adverse event shall be assessed and categorized.

During causality assessment activity, clinical judgement shall be used and the relevant documents, such as the Investigator's Brochure, the Clinical Investigation Plan or the Risk Analysis Report shall be consulted, as all the foreseeable serious adverse events and the potential risks are listed and assessed there. The presence of confounding factors, such as concomitant medication/treatment, the natural history of the underlying disease, other concurrent illness or risk factors shall also be considered.

The above considerations apply also to the serious adverse events occurring in the comparison group.

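### The primary 24-hour and 7-day AE counts are not reproducible as written: onset is listed by date, the time anchor varies, the day-7 cut-off can be read as 5 to 8 days, and the main AE tables state no window

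*SAP*

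**What the plan says.** **Windows.** Protocol 6.2 runs the acute window "up to 24 hours following the transfusion initiation", and SAP 3.1 does the same. For the longer window, SAP 3.1 says "overall, up to 7 days (+/- 1 day) after the transfusion episode", matching protocol 6.2. The outcome in protocol 7.1 reads "within a time frame up to 24 hours following the transfusion and overall up to 7 days (+/- 1 day) after the transfusion", and SAP 3.3.1 reads "from transfusion up to 24 hours and 7 days (+/- 1 day) post transfusion". The rows in SAP 7.8.1 follow the outcome wording, so initiation appears in the objectives only.

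**Exposure.** Under protocol 10.1.1 a patient receives "a transfusion of 2 units of hypoxic RBCs and any additional conventional RBCs as needed". An episode can therefore mix hypoxic and conventional units, and no order is given.

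**Onset.** Protocol 12.2, repeated in 12.6, states: "Documentation of AEs (including SAEs) by the PI includes diagnosis or symptoms, start and stop dates of event". Protocol 12.8.1 lists "The date of the onset of the adverse event". SAP 7.1.3 measures relative day in days and hours, but for an assessment or value; AE onset is not named. It numbers the transfusion date as day 1, as do the flow charts.

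**Contacts.** Protocol 11.2.1 says "patients will be contacted by phone 24 hours and 7 days (+/- 1) after their transfusion visit"; 11.3.5 places the second call 7 (±1) days post-transfusion.

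**Collection and tables.** AEs are collected from consent (protocol 12.2; SAP 6.1.1). The SAP 7.8.1 overview has 24-hour, 7-day, from-enrolment and overall rows. Its SAE, severity, causality and system-organ-class/preferred-term (SOC/PT) presentations state no window. SAP 7.6 and 7.7 give partial-date rules for medical history and medication; SAP 7.1.5 gives none for AEs.

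**The concern.** With no hypothesis and 10 patients per group, the counts are the result, and one patient is 10 percentage points of a group. A count defined in hours needs a start time, an onset time and a fixed end, and the documents settle none of these fully. Most of the gaps can be closed in wording at any time before analysis. The onset time cannot: if the hour of a next-day event was not recorded, it is lost. The 24-hour count is also the part of the primary outcome closest to acute transfusion reactions. Separately, a reader of the SOC/PT or causality tables would take them as AEs after hypoxic red cells, when they may include events that began between consent and transfusion.

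**Working it through.** The only stated figure is the sample size, 10 + 10 = 20, which agrees. SAP 5.1 says it has no statistical basis, so there is no power or alpha to reproduce. The documents give no AE rate; every risk, start time and duration below is an assumption.

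**1. Date-only onset and the 24-hour window.** If the transfusion starts at clock hour *t*, an onset on the next date lies between 24 − *t* and 48 − *t* hours later, and *t*/24 of that date is inside the window.
- Start 08:00: 16 to 40 h; 8/24 = 33% inside.
- Start 16:00: 8 to 32 h; 16/24 = 67% inside.

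The date alone does not classify a next-date AE. By the same arithmetic, *t*/24 of the transfusion date (33% to 67%) precedes the start, so an untimed AE on that date cannot be placed before or after exposure.

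**2. Anchor.** Starting the clock at the end of transfusion instead of at initiation extends the limit by the duration. For assumed durations of 2 to 8 h, 24 h becomes 26 to 32 h from initiation (2/24 = 8% to 8/24 = 33% longer).

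**3. The day-7 cut-off.** The text gives 7 ± 1 days post-transfusion, that is 6 to 8 elapsed days. The flow charts give D7 ± 1 with transfusion on D1; D7 is then 6 elapsed days, so the range is 5 to 7. Together: 5 to 8.

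Let *p* be the assumed 7-day risk and F(d) = 1 − exp(−L·d^k), with L = −ln(1 − p)/7^k. Here k = 1 is constant hazard and k = 0.5 is early clustering. The shift per group of 10 is 10 × [F(d) − F(7)].

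| p | k | 5 days | 6 days | 8 days |
|---|---|---|---|---|
| 0.2 | 1 | −0.53 | −0.26 | +0.25 |
| 0.2 | 0.5 | −0.28 | −0.13 | +0.12 |
| 0.4 | 1 | −0.94 | −0.45 | +0.42 |
| 0.4 | 0.5 | −0.49 | −0.23 | +0.21 |
| 0.6 | 1 | −1.20 | −0.56 | +0.49 |
| 0.6 | 0.5 | −0.61 | −0.28 | +0.25 |

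Example, p = 0.4 and k = 1: F(5) = 0.3057, F(6) = 0.3546, F(7) = 0.4000, F(8) = 0.4422. A one-day shift is 0.12 to 0.56 patient per 10 over the table; a 5-day reading is 0.28 to 1.20.

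**4. Pre-exposure AEs in the main tables.** Take the nominal one day from D0 to D1 and assume the same constant hazard before transfusion. Patients per 10 with such an AE = 10 × [1 − (1 − p)^(1/7)]: 0.31 at p = 0.2, 0.70 at 0.4, 1.23 at 0.6. Those with no AE in the following 7 days are fewer: at p = 0.4, 0.70 × 0.6 = 0.42 per 10, assuming independence.

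**The case against.** The strongest reply is that hour-level timing was evidently intended. SAP 7.1.3 works in days and hours, and the duration variable in SAP 9.4 needs transfusion start and end times. The protocol lists of AE items may be minimum contents, and the CRF and Data Display Plan, which were not available, may hold an onset time and table windows. This stands in part. A reader might infer that onset times are not collected; the documents do not show that. They show only that no listed AE item requires a time, and that SAP 7.1.3 does not name AE onset.

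A reader might also infer that the primary counts include pre-exposure AEs. As worded they do not: SAP 3.3.1 starts at transfusion, and SAP 7.8.1 gives from-enrolment AEs a separate row. Collection from consent is proper and serves a secondary objective. The gap concerns the unwindowed tables, plus any untimed AE on the transfusion date.

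Nor do the documents show that burn patients have only the chart at Day 7. The burn flow charts lack a Day-7 AE mark and a diary row. But the synopsis assigns the diary to both populations, and protocol 11.2.1 and 11.3.5 do not restrict the call by group. That is a conflict to reconcile.

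Finally, the study is descriptive and all AEs will be listed. This limits the harm, but a listing of dates does not supply hours.

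**Conclusion.** The point holds as a definitional weakness that should be fixed. The anchor mismatch, the contact tolerance inside the endpoint, the 5-to-8-day reading and the unwindowed tables are all in the current text; missing onset times are a point to verify.

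The effect is minor to moderate. Under the assumed risks, a one-day shift is worth less than one patient per group of 10, and a 5-day reading about 0.9 at 40% risk with constant hazard. These sizes rest on assumed rates and hazard shapes, and the pre-exposure figure also on an equal hazard before transfusion. No error rate or sample size is affected.

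It would go too far to treat initiation as already governing both windows: the objectives tie only the 24-hour window to it and set the 7-day window after the episode.

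**What to change.** 1. Confirm that the CRF records a clock time for AEs starting on the transfusion date or the next date, and add the field if it does not. Where the time is missing, report the affected counts with and without untimed AEs on either date.
2. State one anchor in the objectives, the outcomes and SAP 7.8.1, for example initiation of the first hypoxic unit. If it also serves the 7-day window, amend protocol 6.2 and SAP 3.1, which now refer to the episode.
3. Define the windows by AE onset at fixed 24 h and 168 h, and keep ±1 day as a contact window only. When the call falls before 168 h, complete the window from the diary and the final chart review. Protocol 5.5 can end AE collection at discharge, at the next transfusion or on Day 28, so report how many patients were followed for the full 168 h.
4. Restrict the SAE, severity, causality and SOC/PT tables to AEs starting at or after the anchor. List earlier AEs separately and keep the planned from-enrolment and overall rows.
5. Reconcile the burn flow charts (protocol synopsis, protocol 11.1.2, SAP Appendix B) with the synopsis intervention entry and protocol 11.2.1 and 11.3.5.

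Cost: possibly one CRF field, plus wording in both documents; no visit needs to be added. If many calls fall before 168 h, more of the 7-day count will rest on diary and chart. Where times are missing, the 24-hour result becomes a range.
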